5.7.4. Eligibility, Demographic, Clinical and Exposure Characteristics

The number and percentage of patients meeting the eligibility criteria will be reported in a subject evaluation table.

Descriptive statistics will be used to summarize patient demographics, clinical characteristics, and healthcare utilization on or prior to index date. Descriptive statistics will be repeated by BNT162b2 vaccination status by the end of follow-up. Standardized mean differences (SMD) will be used to assess covariate balance by BNT162b2 vaccination status by the end of each month of follow-up. Overall SMDs will be presented for each covariate as the maximum absolute value across the months. SMDs ≤0.1 will be considered as evidence of negligible imbalance.

Summaries of the overall follow-up time in months will be presented and calculated as time from index date to the earliest of 6 months of follow-up, end of medical and/or pharmacy enrollment, receipt of a non-Pfizer BioNTech COVID vaccine, receipt of a second BNT162b2 COVID-19 vaccine dose or death.

The number of patients who are BNT162b2 vaccinated by the end of the overall follow-up will be reported. Kaplan-Meier analysis will be used to summarize the percentage of persons who are BNT162b2 vaccinated by the end of each month of follow-up. Patients will be censored at the earliest of the following: 6 months of follow-up, end of medical and/or pharmacy enrollment, receipt of a non-Pfizer BioNTech COVID vaccine or death.

The above analysis will be repeated by age group and state of residence.

5.7.5. Primary Analyses

Unvaccinated and unvaccinated person-time (Section 5.7.3) for each outcome of interest will be calculated for each patient, summed across all patients and presented in person-months. The total number of patients with each of the outcomes will be presented by BNT162b2 vaccination status at the time of the COVID-19 encounter. Crude incidence rates and 95% confidence intervals (CIs) will be presented as events per 100,000 person-months (or as appropriate) by BNT162b2 vaccination status. The above analysis will be presented overall and may also be presented by month of follow-up for the primary and secondary outcomes.

Unadjusted Cox regression models will be used to generate hazard ratios (HR) and 95% CIs for the effect of the BNT162b2 for each outcome, with BNT162b2 modelled as a time-varying exposure. Crude VE percentages will then be estimated based on (1-HR) x 100, where HR is obtained from the unadjusted model.

For the primary outcome, for each of incidence rates and hazard ratios, an additional stratification of interest will employ an interaction term between exposure and a time-varying calendar time covariate, to allow for separate estimates of incidence and hazard in the predominantly XBB (11 September – 08 December 2023), co-circulation

(09 December 2023 – 05 January 2024) and predominantly JN.1 (January 6, 2024 – end of data collection [March 11, 2024]) eras.

Adjusted Cox regression models will also be used to generate adjusted HRs (aHR) and adjusted VE percentages, with covariates listed in Table 5.3 included as time-fixed covariates. For analyses where the number of events per variable is low (Section 5.7.2), covariates with SMDs <0.1 may be excluded from regression models.

Measures of absolute and relative VE: For each outcome above, where sample size allows, results will be calculated as:

- Absolute VE comparing vaccinated to unvaccinated persons, regardless of prior vaccination
- Relative VE will be calculated for each of the following mutually exclusive subgroups.
 - a. XBB.1.5 vaccinated vs XBB.1.5 unvaccinated persons who received BA.4/5 bivalent vaccine (regardless of brand).
 - b. XBB.1.5 vaccinated vs XBB.1.5 unvaccinated persons who did not receive BA.4/5 bivalent vaccine but did receive at least 2 doses of mRNA vaccine (regardless of brand).
 - XBB.1.5 vaccinated vs never COVID-19 vaccinated (of any formulation or brand).

The proportional hazards assumption for the exposure will be assessed graphically with the inspection of Schoenfeld residuals. If the assumption is not met, the follow-up may be restricted up to the time where the assumption is met or VEs may be generated during intervals using piecewise Cox models.

We will further use incidence of the COVID-19 endpoint in unvaccinated persons and apply VE estimates to estimate the number of cases averted per 100,000 person-months. This estimate of the vaccine-preventable disease incidence will be generated for each endpoint as the adjusted VE as a proportion multiplied by the incidence rate among unvaccinated persons.

The above analysis will be repeated by age group for each outcome, subject to patient counts (Section 5.7.2). Additionally, the analysis for the primary outcome will be repeated by state of residence. Subject to the distribution of time since last prior COVID-19 vaccine, relative VEs may also be repeated by subgroups of that variable.

5.7.6. Assessment of Residual Confounding

Negative control outcomes will be used to quantify residual and unmeasured confounding (Table 5.2). The analysis described above will be conducted for the negative control outcomes. Persons with a diagnosis of the negative control outcome within 90 days prior to index date will be excluded from the analysis for that outcome.

In the event aHR for negative control outcomes have a significant effect (95% CI do not include null value of 1), then the set of confounders will be adjusted to allow for calibration. The COVID-19 related outcome VE results may be additionally reported after correcting for estimates of the bias [5].

5.7.7. Sensitivity Analyses

Sensitivity analyses will consider the impact of study design and analytic assumptions, such as varying the exposure definition to 7 days post vaccination rather than 14 days and restricting the follow-up to 3 rather than 6 months.

6. REFERENCES

7. APPENDICES

7.1. Appendix A: Table Shells

The list of planned outputs and table shells will be presented in a separate document.

1. AMENDMENTS FROM PREVIOUS VERSION(S)

NA. First version.

2. LIST OF ABBREVIATIONS

Abbreviation	Definition	
AIC	Akaike information criterion	
CI	Confidence Interval	
CCI	Charlson Comorbidity Index	
CDC	Centers for Disease Control and Prevention	
COPD	Chronic obstructive pulmonary disease	
COVID-19	Coronavirus disease 2019	
CPT	Current Procedural Terminology	
CVX	Clinical Vaccines Administered code	
ED	Emergency department	
HCPCS	Healthcare Common Procedure Coding System	
HCRU	Healthcare resource utilization	
HIPAA	Health Insurance Portability and Accountability Act	
ICD-10-CM	International Classification of Diseases, Tenth Revision, Clinical Modification	
ICU	Intensive care unit	
IMV	Invasive mechanical ventilation	
IPCW	Inverse Probability of Censoring Weighting	
LOS	Length of stay	
NDC	National Drug Codes	
Q1	First quartile, 25 th percentile	

Abbreviation	Definition	
Q3	Third quartile, 75 th percentile	
SAP	Statistical analysis plan	
SD	Standard deviation	
SMD	Standardized mean differences	
UC	Urgent care	
US	United States	
USD	US dollars	

Note: in this document, any text taken directly from the non-interventional study protocol is *italicized*.

3. RATIONALE AND BACKGROUND

Until recently, vaccine registries were not available for de-identification and linkage to secondary claims-based databases. However, through a collaboration with HealthVerity, a leading supplier of secondary health data, the State of California and the State of Louisiana have made their vaccine registries available for linkage for research purposes. California and Louisiana deidentify the registries, using HealthVerity's software to convert each patient's protected health information to a unique HealthVerity ID which can then be linked to the full HealthVerity database to gather clinical history and outcomes.

The purpose of this document is to detail the statistical methods and analyses that will be used in the HealthVerity claims database linked to the State of California/Louisiana's vaccine registries to address Aim 3B of the study protocol. Separate SAPs will be produced to address the other aims of the protocol.

4. STUDY OBJECTIVES AND HYPOTHESES

The objective of Aim 3B of this study is to estimate long-term (3B) healthcare resource utilization and costs associated with COVID-19 by vaccination status, age group and site of care.

This study is descriptive in nature and as such does not include any pre-specified hypotheses.

5. RESEARCH METHODS

5.1. Study Design

This will be a retrospective cohort study using data from patients who were California or Louisiana residents in the HealthVerity claims database.

5.2. Study Population

The study population will be comprised of adult (≥18 years of age) or pediatric (6 months to <18 years of age) patients who were diagnosed with COVID-19 between 01 June 2022 and 30 November 2022 and matched cohorts of control patients, who will be identified as those without a clinical diagnosis of COVID-19 during the matching time period. Patient matching will be described in greater detail in the latter section of the study protocol.

5.2.1. Inclusion Criteria

Patients must meet the following criteria to be eligible for the study:

All Patients:

Aim 3B criteria are different based on the pediatric and adult population analyses as follows:

5.2.1.1. Aim 3B Adult Inclusion Criteria

- 1. Born in 2004 or earlier (as age 18 or older as of the index date, owing to the data providing year but not month or day of birth).
- 2. Has COVID-19 diagnosis (ICD-10-CM code U07.1) in any setting, any position between 01 June 2022 and 30 November 2022 (first eligible code is the index date).
- 3. At least one year of continuous pharmacy and medical enrollment in HealthVerity prior to index date (ie, COVID-19 diagnosis). A gap of up to 30 days will be allowed.
- 4. Have been a State of California/Louisiana resident for at least one year prior to index date (ie, COVID-19 diagnosis)
- 5. Have continuous medical and prescription insurance coverage for at least 30 days after the index date (follow-up period).
 - The duration of the follow-up period will be required to be at least 1 month.
 - NOTE: since the evaluation of the long-term HCRU and cost starts from 1 month after the index date, this requirement for patients to have at least one month of follow-up is needed for this study.

5.2.1.2. Aim 3B Pediatric Inclusion Criteria

- 1. Born in 2005 or later (as age 0-17 years in 2023, owing to the data providing year but not month or day of birth)
- 2. Has COVID-19 diagnosis (ICD-10-CM code U07.1) in any setting, any position between 01 June 2022 and 30 November 2022 (first eligible code is the index date).
- 3. At least six months of pharmacy and medical enrollment in HealthVerity prior to index date. Six months was selected to allow for analysis to include children <1 year due to patient privacy measures in HealthVerity data. A gap of up to 30 days will be allowed
 - So, for the pediatric patients, the minimum age will be 6 months due to this requirement of six months of baseline period.
- 4. Have been a State of California/Louisiana resident for at least six months prior to index date
- 5. Have continuous medical and prescription insurance coverage for at least 30 days after the index date (follow-up period).
 - The duration of the follow-up period will be required to be at least 1 month.

NOTE: since the evaluation of the long-term HCRU and cost starts from 1 month after the index date, this requirement for patients to have at least one month of follow-up is needed for this study.

The index COVID-19 hospitalizations will be identified between 01 June 2022 and 30 November 2022 (COVID identification period)

- To avoid the incidental identification of COVID-19, hospitalizations for COVID-19 were defined as those with an inpatient encounter at an acute care facility with ICD-10-CM code U07.1. Furthermore, hospitalizations did not have an additional incidental code (for unintentional injury, physical trauma, poisoning, short-stay [<2 days] childbirth or serious psychiatric admissions), or a U07.1 hospitalization where treatment used solely for COVID-19 (eg, remdesivir) was identified regardless of accompanying diagnoses.
- The earliest claim will be identified as the index event with the corresponding date (hospital admission date) as the index date.

Patients who were California or Louisiana residents in the HealthVerity claims database will be identified using the following hierarchical definition:

- 1. Have a location of California or Louisiana indicated within their HealthVerity claims enrollment file record.
 - a. Or, have a location other than California or Louisiana in their HealthVerity claims enrollment file record but have one or more records in the California or Louisiana Immunization Registry. Examples include people who previously lived in Texas but moved to California/Louisiana and received a vaccine, or residents of other states who crossed state lines to receive a vaccine in California or Louisiana.

Matched Control Patients:

- 1. Control patients will be exact-matched up to 4:1 to COVID-19 patients using the following matching criteria:
 - a. Control patients will be assigned a random date between 01 June 2022 and 30 November 2022 as the index date. The control patients' index date will be further required to be within the \pm 14 days of the index date of their corresponding matched COVID-19 patients.
 - i. Have continuous medical and prescription insurance coverage between June 1, 2022 and November 30, 2022
 - ii. To ensure that the follow-up period of control patients will not be post-COVID-19, control patients are required to have no COVID-19 diagnoses in any position in any inpatient or outpatient claims prior to 30 November 2022.

- Control patients are allowed to have a COVID-19 diagnosis after 30 November 2022 as long as all other patient matching criteria are met. In such cases, the follow-up period of these control patients will be censored at the date of the first inpatient or outpatient claim with a COVID-19 diagnosis in any position.
- iii. Control patients will have similar continuous insurance enrollment criteria as the COVID-19 patients, described as below:
 - Similar to their matched adult and pediatric COVID-19
 patient counterparts, control patients will be required to have
 12 and 6 months of continuous baseline enrollment,
 respectively.
 - Control patients will be required to have continuous medical and prescription insurance coverage for at least 1 month after the index date (follow-up period).
- Control patients will be matched 4:1 without replacement to COVID-19 patients using the following criteria (exact match unless otherwise specified).
 - i. Index date within ± 14 days of the index date of the COVID-19 patient
 - ii. Age
 - Sample size permitting, an exact match of age will be used.
 If not, matched patients will be required to be within the same age group (see Table 1) AND have an age gap of no more than 2 years (control patient age = COVID-19 patient age ± 2 years).
 - iii. Gender
 - iv. State
 - v. Insurance type at the Index Date
 - vi. Charlson Comorbidity Index (CCI) groups during the baseline period (CCI score of 0, 1, 2, 3+)
 - vii. Groups of the number of all-cause hospitalizations during the baseline period (0, 1, 2, 3+ hospitalizations)
 - viii. Groups of the number of all-cause outpatient visits during the baseline period (0, 1, 2, 3+ outpatient visits)
- The patient matching criteria may be further modified/relaxed if the proposed criteria are too restrictive (ie, collapsing and/or combining criteria).

5.2.2. Exclusion Criteria

Patients meeting any of the following criteria will be excluded from the study analyses:

- Currently pregnant (identified with medical codes during the up to 9 months lookback prior to the index date) or immunocompromised (see algorithm below) at the time of study index
 - Immunocompromised at the time of study index defined as one inpatient and/or 2 outpatient claims 7 days apart for any of:
 - ICD-10-CM codes for HIV/AIDS using all-available lookback
 - ICD-10-CM codes for hematologic malignancy in prior year
 - ICD-10-CM codes for solid organ or bone marrow transplant in prior two years
 - NDC, HCPCS and/or ICD-10-PCS codes for immunosuppressive medication in 210 prior days. Note: 210 days was chosen to add a 30-day grace period to 180 days, given some of the most immunosuppressive medications like rituximab and ocrelizumab are given semi-annually and we wanted to minimize misclassifications due to an overly strict definition.
- 2. Individuals with discrepancies in sex and/or year of birth between HealthVerity claims and California/Louisiana immunization registry datasets.
- 3. Individuals with a diagnosis of COVID-19 in any setting ≤90 days prior to index.
- 4. Individuals who were vaccinated within 13 days prior to the index date.

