8.2.2.4. Aim 3B Exclusion Criteria

For each of adult and pediatric:

- Currently pregnant (using a validated gestational age algorithm with up to 9 months lookback) or immunocompromised (using all-available lookback) at the time of study index (code list to be listed in the appendix)
- Individuals with discrepancies in sex and/or year of birth between HealthVerity claims and California/Louisiana immunization registry datasets.
- Individuals with a diagnosis of COVID-19 in any setting ≤ 90 days prior to index.
- Individuals who were vaccinated within 13 day of index.
- Individuals who had a change in vaccination status changed during follow-up.

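### Aim 3B's two-outpatient-claim rule also covers the drug criterion, so the 210-day window chosen to catch semi-annual drugs can miss most outpatient users billed once per dose

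*SAP*

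**What the plan says.** Section 5.2.2 of the Aim 3B SAP removes people who are immunocompromised at index. The test is "Immunocompromised at the time of study index defined as one inpatient and/or 2 outpatient claims 7 days apart for any of" four listed criteria: HIV/AIDS codes over all available look-back, hematologic malignancy codes in the prior year, transplant codes in the prior two years, and a drug criterion, "NDC, HCPCS and/or ICD-10-PCS codes for immunosuppressive medication in 210 prior days". Nothing exempts the drug criterion from the lead-in.

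The drug criterion carries its own rationale. The SAP says that "210 days was chosen to add a 30-day grace period to 180 days", because "some of the most immunosuppressive medications like rituximab and ocrelizumab are given semi-annually" and "we wanted to minimize misclassifications due to an overly strict definition".

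The protocol's version of this exclusion (section 8.2.2.4) reads "immunocompromised (using all-available lookback) at the time of study index", with no 210-day limit. Protocol section 8.7 allows the SAP to modify protocol plans, so the shorter look-back is not in itself an error.

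**The concern.** A window of one dosing interval plus a grace period is built to find the most recent dose. A rule that needs two outpatient claims has to find the most recent dose and the one before it. With 180-day dosing, both rarely fall within 210 days. The rule and its stated reason therefore work against each other inside a single criterion.

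What is at stake is who enters Aim 3B. A programmer who follows the text will keep some people on the drugs that the SAP singles out as among the most immunosuppressive. Those people can have recurring drug and administration costs during follow-up, and the main outcomes are all-cause costs and resource use compared between COVID-19 patients and matched controls. Neither the matching criteria (section 5.2.1) nor the regression covariates (section 5.6) include an immunosuppression term, although several covariates act as partial proxies.

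**Working it through.** **Inputs, all from Aim 3B SAP section 5.2.2 unless marked**
- Dosing interval: T = 180 days (semi-annual, as the SAP uses it).
- Look-back window: W = 210 days.
- Needed to qualify: one inpatient claim, or two outpatient claims 7 days apart.
- Assumption: each dose leaves one outpatient claim date. The documents give no number of claims per dose or course.
- Assumption: index timing is unrelated to the dosing cycle. For controls, section 5.2.1 assigns a random index date, which supports this. For cases, index is the first eligible COVID-19 code.
- Assumption: no inpatient claim and no qualifying HIV/AIDS, hematologic malignancy or transplant codes.

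**Reproducing the plan's figure.** 180 + 30 = 210 days, as stated.

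**Share caught by the drug criterion.** Let u be the days from the last dose to index, spread evenly over 1 to T. The previous dose was u + T days before index. Both lie in the window only if u + T ≤ W, that is u ≤ W − T. For T ≤ W ≤ 2T:

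share with two claims = (W − T)/T = (210 − 180)/180 = 30/180 = 16.7%

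share missed = 150/180 = 83.3%

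The 7-day separation is met automatically. Counting the index day as part of the window changes the share missed to 149/180 = 82.8%.

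**Other intervals, same formula**

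| Interval T (days) | Two claims in 210 days | Missed |
|---|---|---|
| 168 | 42/168 = 25.0% | 75.0% |
| 180 | 30/180 = 16.7% | 83.3% |
| 182 | 28/182 = 15.4% | 84.6% |
| 200 | 10/200 = 5.0% | 95.0% |

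Simulated irregular intervals (mean 180 days, SD 7 to 21 days) gave 83.0% to 83.3% missed.

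**Relaxing the assumptions**
- If a share q of users qualifies by an inpatient claim or a diagnosis criterion, the share missed is (1 − q) × 5/6: 75% at q = 10%, 67% at q = 20%, 42% at q = 50%.
- If each course is billed on two outpatient dates at least 7 days apart (checked at 14 days), none are missed.

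**What would match the stated purpose**
- One claim sufficient, W = 210: none are missed at any regular interval up to 210 days.
- Two outpatient claims kept, T = 180: the share missed is 66.7% at 240 days, 50% at 270, 33.3% at 300, 16.7% at 330 and 0% at 360.

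The 210-day window thus fits a one-claim rule. A two-claim rule would need about 360 days.

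**The case against.** The strongest reply is that 83% depends on conditions the documents do not establish. A reader might infer that the SAP misses five in six of all users of these drugs. It does not show that. One inpatient claim is enough, the three diagnosis criteria are separate routes in, and billing on two dates at least 7 days apart would remove the problem. The SAP also says only that some medications are semi-annual; drugs claimed more often can meet two claims in 210 days. All of this stands, and the figure must carry its conditions.

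A reader might also infer that the retained patients' drug costs end up in the estimated long-term cost of COVID-19, and try to put a sum on it. The documents do not support that. They give no prevalence of these drugs in either cohort and no cost per user, and with equal shares in the two cohorts there would be no such contribution. The regression models adjust for baseline all-cause allowed amount, Charlson Comorbidity Index, hospitalizations and outpatient visits. Adults have a one-year baseline, so a regular 180-day user would have about two doses (365/180) in that baseline cost. This may reduce any bias, perhaps not fully. The cohort comparisons outside the regression have only the matching, which uses comorbidity and visit groups but not baseline cost. The planned standardized mean differences cover baseline outpatient and pharmacy costs, so an imbalance there would be visible, though not removed.

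Finally, this may be loose drafting, with the two-claim rule meant only for diagnoses. The drug criterion includes NDC codes, while SAP Tables 1 and 2 list pharmacy claims apart from inpatient and outpatient care, so it is unclear what an outpatient claim means for them. That is possible, but it argues for correcting the sentence: as written it would be programmed the other way.

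**Conclusion.** The point holds in a conditional form. The claim-count rule and the reason given for the 210-day window are inconsistent. Among users treated only as outpatients, with one claim date per 180-day dose, index timing unrelated to dosing and no qualifying HIV/AIDS, hematologic malignancy or transplant codes, the drug criterion misses 150/180 = 83%. The share is smaller when other routes apply and can be zero under split billing. Where those conditions hold, patients the SAP intends to exclude remain among both cases and controls. That is a defect in cohort definition; it is not evidence of a biased cost estimate of any known size or direction.

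**What to change.** In section 5.2.2 of the Aim 3B SAP:
- Keep the two-outpatient-claim rule for the three diagnosis-code criteria.
- For the medication criterion, count one claim in any setting within 210 days, at least for administered long-interval agents identified by HCPCS or ICD-10-PCS codes.
- State whether and how an NDC pharmacy claim counts.
- Apply the same rule to cases and controls.

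The cost is a sentence or two in the SAP and a small change to the cohort code. The downside is small: if the one-claim rule is applied to all drugs, some people with a single short course are also excluded. Limiting it to administered long-interval agents reduces that loss. If the sponsor does intend two claims for drugs, the 210-day rationale needs rewriting, because that window does not serve the stated purpose.
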